9.1.13 Contraception and Pregnancy Avoidance Procedure

From signing of informed consent, throughout the duration of the study, to the end of the follow-up period, female subjects of childbearing potential (e.g., non-sterilized or premenopausal female subjects) who are sexually active with a nonsterilized male partner must use adequate contraception. Subjects will be provided with information on acceptable methods of contraception as part of the subject informed consent process and will be asked to sign a consent form stating that they understand the requirements for avoidance of pregnancy during the course of the study. During the course of the study, regular urine human chorionic gonadotropin (hCG) pregnancy tests will be performed, and subjects will receive continued guidance with respect to the avoiding pregnancy as part of the study procedures ([Appendix A](#)).

At visits when pregnancy tests are performed, subjects must be confirmed of having a negative urine hCG pregnancy test, as well as at the follow-up examination.

9.1.14 Pregnancy

If any subject is found to be pregnant during the study she should be withdrawn and any study medication should be immediately discontinued.

If the pregnancy occurs during administration of active study medication from the start of the study medication in the double-blind treatment period to the end of the follow-up period, the pregnancy should be reported immediately, using a pregnancy notification form, to the contact listed in the attachment.

Should the pregnancy occur during or after administration of blinded drug, the investigator must inform the subject of their right to receive treatment information. If the subject chooses to receive unblinded treatment information, the individual blind should be broken by the investigator. Subjects randomized to placebo need not be followed.

If the female subject agrees to the primary care physician being informed, the investigator should notify the primary care physician (obstetrics and gynecology specialist) that the subject was participating in a clinical study at the time she became pregnant and provide details of treatment the subject received (blinded or unblinded, as applicable).

All pregnancies will be followed up to final outcome, using the pregnancy form. The outcome, including any premature termination, must be reported to the sponsor. An evaluation after the birth of the child will also be conducted.

9.1.15 ECG Procedure

A standard 12-lead ECG will be recorded. The investigator (or a qualified observer at the study site) will interpret the ECG using 1 of the following categories: within normal limits, abnormal but not clinically significant, or abnormal and clinically significant. The following parameters will be recorded on the eCRF from the subject's ECG trace: RR interval, PR interval, QT interval, QRS interval, and QTcB interval. QTcF interval will be calculated by the sponsor. ECG traces recorded on thermal paper should be photocopied to avoid degradation of trace over time.

9.1.16 Pharmacogenomic Sample Collection

One 5-mL whole blood sample for pharmacogenomics will be collected at the start of placebo lead-in period (Visit 2) or at the earliest possible time during the study from subjects who signed informed consent of pharmacogenomics and entered into the placebo lead-in period for possible exploratory investigation of markers enabling the prediction of drug response.

Pharmacogenomic sample should not be collected from any subject who has received comparable bone marrow transplant or whole blood transfusion within 6 months of any sample collection.

See the separately created procedure for collecting, handling, and storage of pharmacogenomic samples.

9.1.17 Pharmacokinetic Sample Collection and Analysis

9.1.17.1 Collection of Blood for Pharmacokinetic Sampling

Blood samples will be collected in concurrence with blood collection for clinical laboratory tests. The exact date and time of the blood collection and dosing times of the last 2 doses prior to the blood collection will be recorded on the eCRF. Refer to the separately created procedure for collection, handling, and shipping of blood samples.

Since drug concentrations of subjects in the placebo group will not be measured, the assignment personnel will send an operation manual to the central laboratory to identify samples of subjects in the placebo group. Drug concentration data will be reported to the sponsor after unblinding of the study.

9.1.17.2 Bioanalytical Methods

Plasma concentrations of Lu AA21004 and its metabolites (Lu AA34443 and Lu AA39835) will be analyzed with the validated LC/MS/MS method.

9.1.18 Documentation of Screen Failure Prior to Entrance into Placebo Lead-in Period

For all subjects who signed informed consent and prematurely discontinue the study prior to entry into the placebo lead-in period, the investigator should complete the eCRF. The registration center should be contacted as a notification of screen failure prior to entry into the placebo lead-in period.

The primary reason for screen failure prior to entry into the placebo lead-in period will be recorded in the eCRF using the following categories:

- PTE/AE
- Did not meet inclusion criteria or did meet exclusion criteria <specify the reason.>
- Significant protocol deviation
- Lost to follow-up
- Voluntary withdrawal <specify the reason.>
- Study termination
- Other <specify the reason.>

The identification numbers assigned to subjects who prematurely discontinues prior to entry into the placebo lead-in period should not be reused.

9.1.19 Documentation of Study Entrance into Placebo Lead-in Period

Only subjects who meet all of the inclusion criteria and none of the exclusion criteria at the start of placebo lead-in period are eligible for entrance into the placebo lead-in period.

If the subject is found to be not eligible for the placebo lead-in period, the investigator should record the primary reason for failure on the applicable eCRF.

9.1.20 Documentation of Screen Failure Prior to Randomization

For all subjects who prematurely discontinue the study after entry into the placebo lead-in period and prior to randomization, the investigator should complete the eCRF. The registration center should be contacted as a notification of discontinuation after entry into the placebo lead-in period and prior to randomization.

The primary reason for screen failure after entry into the placebo lead-in period and prior to randomization is recorded in the eCRF using the following categories:

- PTE/AE
- Did not meet inclusion criteria or did meet exclusion criteria <specify the reason.>
- Significant protocol deviation
- Lost to follow-up
- Voluntary withdrawal <specify the reason.>
- Study termination
- Other <specify the reason.>

The end-of-study evaluation will be performed for all subjects who prematurely discontinue the study after entry into the placebo lead-in period and prior to randomization according to Section [9.3.5](#).

9.1.21 Documentation of Randomization

Only subjects who meet all of the inclusion criteria and none of the exclusion criteria are eligible for randomization and entrance into the double-blind treatment period.

If the subject is found to be not eligible for randomization, the investigator should record the primary reason for screen failure on the eCRF.

9.2 Monitoring Subject Treatment Compliance

Subjects will be required to bring unused study medication containers (PTP sheets)/unused medications to each dispensing site visit. The dates of the initial and last dosing, as well as any details where a subject takes more or less of the study medications than the specified dose, will be recorded on the eCRF.

If a subject is significantly noncompliant with the study medication (e.g., 6 or more consecutive doses missed), it may be appropriate to withdraw the subject from the study. All subjects should be re instructed about the dosing requirement during study contacts. The authorized study personnel conducting the re-education must document the process in the subject source records.

9.3 Schedule of Observations and Procedures

The schedule for all study-related procedures for all evaluations is shown in [Appendix A](#). Assessments should be completed at the designated visit/time point(s).

9.3.1 Screening Period

Informed consent must be obtained prior to the initiation of any study procedures.

The examinations/observations/assessments listed below will be performed at the start of screening period (Days -32 to -12; Visit 1). Subjects will be screened in accordance with predefined inclusion and exclusion criteria as described in Section [7.0](#). See Section [9.1.18](#) for procedures for documenting a subject who prematurely discontinues the study prior to entry into the placebo lead-in period.

- Demographics, medical history, and medication history
- Diagnosis of MDD
- Assessments of the major depressive episode
- Physical examination
- Weight and height
- Vital signs

- Concomitant medications
- Concurrent medical conditions
- Clinical laboratory tests
- Pregnancy test (female subjects of childbearing potential only)
- Urine drug screening
- ECG procedure
- C-SSRS
- PTE assessment
- MADRS
- HAM-D
- CGI-S

9.3.2 Placebo Lead-in Period

The examinations/observations/assessments listed below will be performed at the start of placebo lead-in period (Day -8 ± 3 ; Visit 2). Subjects will be screened in accordance with predefined inclusion and exclusion criteria as described in Section 7.0. Subjects assessed to be eligible will enter the placebo lead-in period. See Section 9.1.18 for procedures for documenting subjects who prematurely discontinue the study prior to entry into the placebo lead-in period.

- Physical examination
- Weight
- Vital signs
- Concomitant medications
- Clinical laboratory tests (fasted)
- Pregnancy test (female subjects of childbearing potential only)
- Urine drug screening.
- Blood sampling for pharmacogenomics* (subjects who provided written consent only)
- ECG procedure
- C-SSRS
- PTE assessment
- MADRS
- HAM-D

- CGI-S
- SDS
- DSST
- PDQ-5
- QIDS-J
- Dispense of the study medication (for the placebo lead-in treatment)

* Blood sampling for pharmacogenomics will be performed at the start of placebo lead-in period (Visit 2) or at the earliest possible time during the study.

9.3.3 Start of Double-blind Treatment Period/Randomization

The examinations/observations/assessments listed below will be performed at the start of double-blind treatment period (Day -1; Visit 3). Subjects will be screened in accordance with predefined inclusion and exclusion criteria as described in Section 7.0. Subjects assessed to be eligible will be randomized according to Section 8.2 and enter the double-blind treatment period. See Section 9.1.20 for documenting subjects who prematurely discontinue the study after entry into the placebo lead-in period and prior to randomization.

The examinations/observations/assessments at Visit 3 should be regarded as baseline evaluations.

- Physical examination
- Weight
- Vital signs
- Concomitant medications
- Clinical laboratory tests (fasted)
- Pregnancy test (female subjects of childbearing potential only)
- ECG procedure
- C-SSRS
- PTE/AE assessment
- MADRS
- HAM-D
- CGI-S
- CGI-I (assessed comparing with a CGI score at Visit 2).
- SDS
- DSST

- PDQ-5
- QIDS-J
- Randomization
- Dispense of the study medication (for the double-blind treatment [Inner Carton 1])
- Collection of the study medication dispensed at the last visit/Consultation about subjects' compliance

9.3.4 Double-blind Treatment Period

Visit 4

The examinations/observations/assessments listed below will be performed at 1 week after the start of double-blind treatment period (Day 7 ± 1; Visit 4).

- Vital signs
- Concomitant medications
- C-SSRS
- PTE/AE assessment
- MADRS
- CGI-S
- CGI-I (assessed comparing with a CGI score at Visit 3).
- DSST
- PDQ-5
- QIDS-J
- Dispense of the study medication (for the double-blind treatment [Inner Carton 2])
- Collection of the study medication dispensed at the last visit/Consultation about subjects' compliance

Visit 5

The examinations/observations/assessments listed below will be performed at 2 weeks after the start of double-blind treatment period (Day 14 ± 3; Visit 5).

- Vital signs
- Concomitant medications
- C-SSRS
- PTE/AE assessment

- MADRS
- CGI-S
- CGI-I (assessed comparing with a CGI score at Visit 3).
- QIDS-J
- Dispense of the study medication (for the double-blind treatment [Inner Carton 2])
- Collection of the study medication dispensed at the last visit/Consultation about subjects' compliance

Visit 6

The examinations/observations/assessments listed below will be performed at 4 weeks after the start of double-blind treatment period (Day 28 ± 3; Visit 6).

- Weight
- Vital signs
- Concomitant medications.
- Clinical laboratory tests
- Pregnancy test (female subjects of childbearing potential only)
- Pharmacokinetic sampling
- ECG procedure
- C-SSRS
- PTE/AE assessment
- MADRS
- CGI-S
- CGI-I (assessed comparing with a CGI score at Visit 3).
- QIDS-J
- Dispense of the study medication (for the double-blind treatment [Inner Carton 2])
- Collection of the study medication dispensed at the last visit/Consultation about subjects' compliance

Visit 7

The examinations/observations/assessments listed below will be performed at 6 weeks after the start of double-blind treatment period (Day 42 ± 3; Visit 7).

- Vital signs

- Concomitant medications
- C-SSRS
- PTE/AE assessment
- MADRS
- CGI-S
- CGI-I (assessed comparing with a CGI score at Visit 3).
- QIDS-J
- Dispense of the study medication (for the double-blind treatment [Inner Carton 2])
- Collection of the study medication dispensed at the last visit/Consultation about subjects' compliance

9.3.5 End of Double-blind Treatment Period or Early Termination

The examinations/observations/assessments listed below will be performed at 8 weeks after the start of double-blind treatment period (Day 56 ± 3; Visit 8) as evaluation at the end of double-blind treatment period. Subjects who prematurely discontinue the study during the placebo lead-in period or double-blind treatment period will be requested to visit the study site for early termination examinations/observations/assessments within 7 days after the day of study discontinuation wherever possible.

- Physical examination
- Weight
- Vital signs
- Concomitant medications
- Clinical laboratory tests (fasted)
- Pregnancy test (female subjects of childbearing potential only)
- Pharmacokinetic sampling (not performed at early termination)
- ECG procedure
- C-SSRS
- PTE/AE assessment
- MADRS
- HAM-D
- CGI-S
- CGI-I*

- SDS
- DSST
- PDQ-5
- QIDS-J
- Collection of the study medication dispensed at the last visit/Consultation about subjects' compliance

* The CGI-I score will be assessed comparing with that at Visit 3. However, at early termination prior to Visit 3, the CGI-I score will be assessed by comparing with that at Visit 2.

For all randomized subjects, the investigator must complete the End of Study eCRF page.

After evaluation at the end of double-blind treatment period or early termination, standard therapy may be performed as needed.

9.3.6 Follow-up Period

A safety follow-up assessment will be conducted at 12 weeks after the start of double-blind treatment period (Day 84 ± 5). For subjects who prematurely discontinue the study during the placebo lead-in period or double-blind treatment period, the follow-up assessments will be made 28 ± 5 days after the last dose of the study medication. The follow-up assessments may either be conducted as a visit to the site or as a telephone contact. In the follow-up, the following will be assessed: outcomes of AEs continuing at Visit 8 or early termination visit, new SAEs developing during the follow-up period, and special interest AEs will be assessed. Female subjects of child-bearing potential will be asked to confirm whether they are pregnant or not.

9.3.7 Post Study Care

The study medication will not be available upon completion of the subject's participation in the study.

9.4 Biological Sample Retention and Destruction

Samples of 5-mL whole blood collected for pharmacogenomics will be stored frozen at the pharmacogenomic specimen storage facility (see the contact listed in the attachment 1; hereinafter referred to as specimen storage facility).

The collected samples will be retained for 20 years from the day when a first pharmacogenomic sample was collected during the study.

When subjects request disposal of a stored sample during the retention period, the site will ask the specimen storage facility to destroy the sample via the sponsor according to the procedure. The specimen storage facility will destroy the sample in accordance with the procedure, and notify the site and sponsor. However, any samples should not be destroyed if all the documents (including medical records) have been destroyed which could identify the subject, and it is impossible to link the sample to the subject.

Even if the sample can be linked to the subject, when pharmacogenomic investigation has been conducted, the remaining sample will be destroyed and the results of pharmacogenomic investigation of the anonymized subject will be retained by the sponsor.

The sponsor will build a management system required for protection of the subject's personal information, define standards for collecting, storage, and destruction of samples, and prepare appropriate procedures.

10.0 PRETREATMENT EVENTS AND ADVERSE EVENTS

10.1 Definitions

10.1.1 PTEs

A PTE is defined as any untoward medical occurrence in a clinical investigation subject who has signed informed consent to participate in a study but prior to administration of any study medication; it does not necessarily have to have a causal relationship with study participation.

10.1.2 AEs

An AE is defined as any untoward medical occurrence in a clinical investigation subject administered a drug; it does not necessarily have to have a causal relationship with this treatment.

An AE can therefore be any unfavorable and unintended sign (e.g., a clinically significant abnormal laboratory finding), symptom, or disease temporally associated with the use of a drug whether or not it is considered related to the drug.

10.1.3 Additional Points to Consider for PTEs and AEs

An untoward finding generally may:

- Indicate a new diagnosis or unexpected worsening of a pre-existing condition. (Intermittent events for pre-existing conditions underlying disease should not be considered PTEs or AEs.)
- Necessitate therapeutic intervention.
- Require an invasive diagnostic procedure.
- Require discontinuation or a change in dose of study medication or a concomitant medication.
- Be considered unfavorable by the investigator for any reason.
- PTEs/AEs caused by a study procedure (e.g., a bruise after blood draw) should be recorded as a PTE/AE.

Diagnoses vs. signs and symptoms:

- Each event should be recorded to represent a single diagnosis. Accompanying signs (including abnormal laboratory values or ECG findings) or symptoms should NOT be recorded as additional AEs. If a diagnosis is unknown, sign(s) or symptom(s) should be recorded appropriately as a PTE(s) or as an AE(s).

Laboratory values and ECG findings:

- Changes in laboratory values or ECG parameters are only considered to be PTEs or AEs if they are judged to be clinically significant (i.e., if some action or intervention is required or if the investigator judges the change to be beyond the range of normal physiologic fluctuation). A laboratory re-test and/or continued monitoring of an abnormal value are not considered an

intervention. In addition, repeated or additional noninvasive testing for verification, evaluation, or monitoring of an abnormality is not considered an intervention.

- If abnormal laboratory values or ECG findings are the result of pathology for which there is an overall diagnosis (e.g., increased creatinine in renal failure), the diagnosis only should be reported appropriately as a PTE or as an AE.

Pre-existing conditions:

- Of pre-existing conditions (present at the time of signing of informed consent), events that are considered accompanying symptoms of MDD should NOT be recorded as concurrent medical conditions, PTEs, or AEs.
- Other pre-existing conditions are considered concurrent medical conditions and should NOT be recorded as PTEs or AEs. Baseline evaluations (e.g., laboratory tests, ECG, X-rays) should NOT be recorded as PTEs unless related to study procedures. However, if the subject experiences an abnormality (e.g., internal bleeding due to blood sampling) associated with the baseline evaluations, the abnormality should be recorded as a PTE and recorded on eCRF. If the subject experiences a worsening or complication of such a concurrent condition, the worsening or complication should be recorded appropriately as a PTE (worsening or complication occurs before start of study medication) or an AE (worsening or complication occurs after start of study medication). The investigator should ensure that the event term recorded captures the change in the condition (e.g., “worsening of hypertension”).
- If a subject has a pre-existing episodic condition (e.g., asthma, epilepsy) any occurrence of an episode should only be captured as a PTE/AE if the episodes become more frequent, serious or severe in nature, that is, the investigator should ensure that the AE term recorded captures the change in the condition from Baseline (e.g., “worsening of...”).
- If a subject has a degenerative concurrent condition (e.g., cataracts, rheumatoid arthritis), worsening of the condition should only be captured as a PTE/AE if occurring to a greater extent to that which would be expected. Again, the investigator should ensure that the AE term recorded captures the change in the condition (e.g., “worsening of...”).

Worsening of PTEs or AEs:

- If the subject experiences a worsening or complication of a PTE after starting administration of the study medication, the worsening or complication should be recorded appropriately as an AE. The investigator should ensure that the AE term recorded captures the change in the condition (e.g., “worsening of...”).
- If the subject experiences a worsening or complication of an AE after any change in study medication, the worsening or complication should be recorded as a new AE. The investigator should ensure that the AE term recorded captures the change in the condition (e.g., “worsening of...”).

Changes in severity of AEs /Serious PTEs:

- If the subject experiences changes in severity of an AE/serious PTE, the event should be captured once with the maximum severity recorded.

Preplanned surgeries or procedures:

- Preplanned procedures (surgeries or therapies) that were scheduled prior to signing of informed consent are not considered PTEs or AEs. However, if a preplanned procedures is performed early (e.g., as an emergency) due to a worsening of the pre-existing condition, the worsening of the condition should be captured appropriately as a PTE or an AE. Complications resulting from any planned surgery should be reported as AEs.

Elective surgeries or procedures:

- Elective procedures (e.g., cosmetic surgery) performed where there is no change in the subject's medical condition should not be recorded as PTEs or AEs, but should be documented in the subject's source documents. Complications resulting from an elective surgery should be reported as AEs.

Insufficient clinical response (lack of efficacy):

- Insufficient clinical response, efficacy, or pharmacologic action, should NOT be recorded as an AE. The investigator must make the distinction between exacerbation of pre-existing illness and lack of therapeutic efficacy.

Overdose:

- All cases of overdose with any medication, including the case without manifested side effects, are considered AEs and will be recorded on the AE page of the eCRF. In addition, cases of overdose will be reported as special interest AEs.

Suicidality events:

- A completed suicide is always captured as an SAE based on its fatal outcome. Furthermore, active suicidal behavior such as suicidal ideation with a specific plan and suicide attempt will also be collected as an SAE.
- Unless the event in question meets the definition of "serious," suicidal thoughts or suicidal ideation without a specific plan or action will be collected as a non-serious AE in accordance with the standard AE reporting requirements.
- A subject who presents with self-mutilation should be asked by the investigator to clarify whether the subject was attempting suicide. If the subject was attempting suicide, the behavior will be collected as an SAE, and the specific suicidal behavior (e.g., wrist cutting) will be recorded in the eCRF. If the subject was not attempting suicide, the behavior will be collected as a non-serious AE in accordance with the standard AE reporting requirements.

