10.1.4 SAEs

An SAE is defined as any untoward medical occurrence that at any dose:

CONFIDENTIAL

1. Results in DEATH.
2. Is LIFE THREATENING.*
3. Requires inpatient HOSPITALIZATION or prolongation of existing hospitalization.
4. Results in persistent or significant DISABILITY/INCAPACITY.
5. Leads to a CONGENITAL ANOMALY/BIRTH DEFECT.
6. Is an IMPORTANT MEDICAL EVENT that satisfies any of the following:
 - May require intervention to prevent items 1 through 5 above.
 - May expose the subject to danger, even though the event is not immediately life threatening or fatal or does not result in hospitalization.
 - Includes any event or synonym described in the Takeda Medically Significant AE List ([Table 10.a](#)).

* The term “life threatening” refers to an event in which the subject was at risk of death at the time of the event; it does not refer to an event that hypothetically might have caused death if it were more severe.

Table 10.a Takeda Medically Significant AE List

Term	
Acute respiratory failure/acute respiratory distress syndrome (ARDS)	Hepatic necrosis
Torsade de pointes / ventricular fibrillation / ventricular tachycardia	Acute liver failure
Malignant hypertension	Anaphylactic shock
Convulsive seizure (including seizure and epilepsy)	Acute renal failure
Agranulocytosis	Pulmonary hypertension
Aplastic anemia	Pulmonary fibrosis (including interstitial lung disease)
Toxic epidermal necrolysis/Stevens-Johnson syndrome	Neuroleptic malignant syndrome / malignant hyperthermia
	Spontaneous abortion / stillbirth and fetal death
	Confirmed or suspected transmission of infectious agent by a medicinal product
	Confirmed or suspected endotoxin shock

The following events are also to be considered SAEs.

- Completed suicide
- Active suicidal ideation
- Active suicidal behavior such as suicide attempt
- Self-injury with suicide attempt

PTEs that fulfill 1 or more of the serious criteria above are also to be considered SAEs and should be reported and followed up in the same manner (see Sections [10.2.2](#) and [10.3](#)).

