10.2 Procedures

10.2.1 Collection and Reporting of AEs

10.2.1.1 PTE and AE Collection Period

Collection of PTEs will commence from the time the subject signs the informed consent to participate in the study and continue until the subject is first administered study medication in the

placebo lead-in period. For subjects who discontinue prior to the first study medication administration in the placebo lead-in period, PTEs are collected until the subject discontinues study participation.

Collection of AEs will commence from the time that the subject is first administered study medication in the placebo lead-in period. Routine collection of AEs will continue until Visit 8 or Early Termination Visit.

Collection of SAEs or special interest AEs will continue until the end of the follow-up period.

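### Protocol Sections 10.1.3 and 10.1.4 classify a serious case of self-mutilation without suicidal intent in opposite ways, and nothing says which prevails

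*Protocol*

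**What the plan says.** Protocol Section 10.1.3 has three bullets on suicidality events.

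- The first makes completed suicide, suicide attempt and ideation with a specific plan SAEs.
- The second makes ideation without a plan or action a non-serious AE, but opens with a condition: "Unless the event in question meets the definition of" serious.
- The third says: "A subject who presents with self-mutilation should be asked by the investigator to clarify whether the subject was attempting suicide". If so, the event is an SAE. If not: "If the subject was not attempting suicide, the behavior will be collected as a non-serious AE". The sentence ends by referring to the standard AE reporting requirements and states no exception.

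Section 10.1.4 starts from outcome: "An SAE is defined as any untoward medical occurrence that at any dose" meets one of six criteria. Among them are "Is LIFE THREATENING", "Requires inpatient HOSPITALIZATION or prolongation of existing hospitalization" and important medical event. Intent plays no part in these criteria. A further list of events that also count as SAEs names "Self-injury with suicide attempt" and does not mention self-injury without an attempt.

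On collection, Section 10.2.1.1 ends routine AE collection at Visit 8 or early termination, and adds: "Collection of SAEs or special interest AEs will continue until the end of the follow-up period". The text is the same in all three protocol editions in the file, including the current one.

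**The concern.** The self-mutilation bullet sets seriousness by the subject's answer about intent. Section 10.1.4 sets it by what happened to the subject. The two agree for minor injuries. They part where it matters most: an injury that is life-threatening or needs admission, in someone who denies wanting to die.

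An investigator could reasonably follow 10.1.3. It is the specific instruction for this event, whereas 10.1.4 is general. The neighbouring bullet has the seriousness exception and this one lacks it, which can look deliberate. The added list in 10.1.4 names self-injury only together with a suicide attempt.

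Two sites could then report the same hospitalised event differently, in a depression trial where self-harm is a central safety question. Section 11.0 provides no data safety monitoring committee, so prompt SAE reporting carries more of the weight.

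**Working it through.** No formula applies, and the plan states no figure to reproduce. The check is to follow one test case through both sections: a subject on double-blind drug cuts himself or herself, is admitted to hospital, and denies suicidal intent.

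| Step | 10.1.3 applied literally | 10.1.4 governs |
|---|---|---|
| Seriousness entered for the event (Protocol 10.2.1.2, item 9) | Non-serious | Serious, by hospitalisation |
| Report within 1 business day (Protocol 10.2.2) | Not triggered | Triggered |
| SAP 3.1.1 items 5 to 7, as applicable | Absent | Counted |
| SAP 3.1.2 table (8), serious TEAEs by SOC and PT | Absent | Counted |
| All-TEAE and intensity tables (SAP 3.1.1 items 1 and 3; SAP 3.1.2 tables 1 and 5) | Counted, if it occurred by Visit 8 | Counted |
| C-SSRS non-suicidal self-injury (SAP 3.3.2.3 and 3.3.2.4) | Counted, if elicited at a scheduled assessment | Same |
| New event after Visit 8 or early termination (Protocol 10.2.1.1 and 9.3.6) | Not collected | Collected to the end of follow-up |

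**Which column applies?** No sentence in the protocol ranks the two sections, so both columns remain open.

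**Does special-interest status rescue the event?** No. Section 10.1.5 lists skin reaction, allergic reaction, hepatic impairment and overdose. Self-mutilation is not among them. Medication overdose is, whatever the intent, so it is reported within 1 business day (10.2.1.3) and collected to the end of follow-up. It is outside this point.

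**Does the C-SSRS rescue it?** Only in part. Section 10.2.1.2 says the scale is not a primary means of collecting AEs, and Appendix A does not schedule it at the follow-up contact.

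**Length of the uncovered window.** Visit 8 is Day 56 and the follow-up contact is Day 84 (Appendix A). For a completer that is 84 − 56 = 28 days, or 28/84 = one third of the period from first double-blind dose to follow-up. This is a length of time, not a probability of an event.

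**Weight of one case.** If an arm's safety set has the planned 160 subjects, one reclassified case changes its serious-TEAE percentage by 1/160 = 0.6 points. This is a scale, not an estimate.

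**The case against.** The strongest reply is that 10.1.4 already settles the matter. Its definition covers any untoward medical occurrence and does not exclude self-injury. The extra list is introduced as an addition to the criteria, so naming only self-injury with an attempt does not narrow them. Seriousness is recorded for every event. The self-mutilation sentence also ends by referring to the standard AE reporting requirements, which can be read to mean that such behaviour is not automatically serious and that the usual criteria then apply.

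Much of this stands. It shows that the literal override is only one reading, so every consequence in the left-hand column of the table is conditional. It does not remove the conflict. The ideation bullet ends with the same reference to standard requirements, yet its drafters still put the seriousness condition in front. By the protocol's own usage, that reference does not do the work of the exception. The seriousness item in 10.2.1.2 records a classification; it does not say which section decides it.

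A reader might also infer that such a case would vanish from the safety report. The documents do not support that: a treatment-emergent event collected by Visit 8 stays in the all-TEAE and intensity tables, and the C-SSRS summaries tabulate non-suicidal self-injury whatever the AE seriousness.

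**Conclusion.** The protocol is wrong as written on this point: two sections give opposite classifications for the same event, and no rule of precedence is stated. If a site follows 10.1.3 literally, a hospitalised or life-threatening case of self-mutilation without suicidal intent may not be expedited, may be missing from the serious-TEAE summaries and, if new after Visit 8 or early termination, may not be collected.

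The conclusion rests on one assumption: that at least some investigators would treat the specific bullet as controlling. If all of them apply 10.1.4, nothing is lost.

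Three stronger inferences should be resisted.

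- The protocol does not direct that these cases go unreported. That would require 10.1.3 to override 10.1.4, and nothing says it does.
- Not every form of self-injury is affected. The bullet covers self-mutilation, and medication overdose has its own route.
- The suicidal ideation rates quoted from the previous Japanese study in Section 4.1.3 (6.6% at 10 mg, 1.6% on placebo) are not self-injury rates. The C-SSRS category in the SAP shows that the scale has such an item, not that events are expected.

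The documents give no rate for non-suicidal self-injury, so the expected number of misclassified cases cannot be estimated.

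**What to change.** Reconcile the two sections by giving the self-mutilation bullet the condition its neighbour already has. For example, end the sentence with: *unless the event meets the definition of serious in Section 10.1.4, in which case it is collected and reported as an SAE*. Carry the same clause into site guidance.

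This uses a condition the protocol already contains. The collection windows and SAP tables need no edit, because they follow the seriousness classification. The cost is one clause and possibly a few more SAE forms.
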